Liver Enzyme Elevations: Confirmed increases in liver enzymes greater than 3 times the upper limit of normal (3× ULN) were observed in patients treated with XELJANZ. In patients experiencing liver enzyme elevation, modification of treatment regimen, such as reduction in the dose of concomitant DMARD, interruption of XELJANZ, or reduction in XELJANZ dose, resulted in decrease or normalization of liver enzymes.

In the controlled monotherapy trials (0–3 months), no differences in the incidence of ALT or AST elevations were observed between the placebo, and XELJANZ 5 mg, and 10 mg twice daily groups.

In the controlled background DMARD trials (0–3 months), ALT elevations greater than 3× ULN were observed in 1.0%, 1.3% and 1.2% of patients receiving placebo, 5 mg, and 10 mg twice daily, respectively. In these trials, AST elevations greater than 3× ULN were observed in 0.6%, 0.5% and 0.4% of patients receiving placebo, 5 mg, and 10 mg twice daily, respectively.

One case of drug-induced liver injury was reported in a patient treated with XELJANZ 10 mg twice daily for approximately 2.5 months. The patient developed symptomatic elevations of AST and ALT greater than 3× ULN and bilirubin elevations greater than 2× ULN, which required hospitalizations and a liver biopsy.

Lipid Elevations: In the controlled clinical trials, dose-related elevations in lipid parameters (total cholesterol, LDL cholesterol, HDL cholesterol, triglycerides) were observed at one month of exposure and remained stable thereafter. Changes in lipid parameters during the first 3 months of exposure in the controlled clinical trials are summarized below:

- Mean LDL cholesterol increased by 15% in the XELJANZ 5 mg twice daily arm
- Mean HDL cholesterol increased by 10% in the XELJANZ 5 mg twice daily arm
- Mean LDL/HDL ratios were essentially unchanged in XELJANZ-treated patients.

In a controlled clinical trial, elevations in LDL cholesterol and ApoB decreased to pretreatment levels in response to statin therapy.

In the long-term safety population, elevations in lipid parameters remained consistent with what was seen in the controlled clinical trials.

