7.5.1 Adverse Events of Special Interest

Included in the secondary outcome analysis are the adverse events of special interest (AESI). The adverse events of interest include but are not limited to:

Gastrointestinal perforations	Patients presenting with new onset abdominal symptoms should be evaluated promptly for early identification of gastrointestinal perforations and report SAE if event meets criteria.
Herpes Zoster	Though infection Herpes is a separate event of interest for this study.
Malignancy	Solid cancers, lymphoma, and non-melanoma skin cancer.
Serious Infections	Serious infections due to bacterial, mycobacterial, invasive fungal, viral, or other opportunistic pathogens. Examples of these would include: pneumonia, cellulitis, urinary tract infection, and diverticulitis, tuberculosis and other mycobacterial infections, cryptococcosis, esophageal candidiasis, pneumocystosis, multidermatomal, cytomegalovirus, and BK virus.
Lab value abnormalities compared to screening at any time point and confirmed by repeat testing	
 1. Lymphocyte count less than 500 cells/mm³ 2. ANC less than 500 cells/mm³ 3. AST/ALT >3 ULN 4. Hy's law= ALT > 3x ULN + bilirubin > 2x ULN 5. A drop of Hb by >2 gm/dL 6. Hb ≤ 8 gm/dL 7. Increase in LDL or HDL >50% 8. Increase in serum creatinine >50%

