7.8 Laboratory Monitoring

A lab monitor will provide oversight and will review subject labs in a blinded manner. The following lab values would result in dose reduction/discontinuation of study drug:

1. Lymphocyte count less than 500 cells/mm³ and confirmed by repeat testing: discontinue drug.
2. Neutropenia. ANC 500–1000 cells/mm³: For persistent decreases in this range, interrupt dosing until ANC is greater than 1000 cells/mm³. When greater than 1000 cells/mm³, resume dose.
3. ANC less than 500 cells/mm³: discontinue drug
4. Low Hemoglobin. Greater than 2 g/dL decrease or less than 8.0 g/dL: discontinue drug until values have normalized.

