1.2. Secondary Endpoints

1.2.1. Secondary Endpoint. Analyses of the Primary Endpoint Over Time.

The analyses of the primary endpoint described in sections 1.1.1 and 1.1.2 will be repeated at Weeks 12 to assess the time course of the safety profile as defined by the occurrence of Grade 3 or higher adverse events.

1.2.2. Secondary Endpoint. Analyses of the Adverse Events at the Grade 2 Threshold.

The analyses described in sections 1.1.1, 1.1.2 and 1.2.1 will be repeated for adverse events beginning at or before the time point of interest that are assessed as at least Grade 2 (moderate) severity.

1.2.3. Secondary Endpoint. % of Subjects with Adverse Events of Special Interest (AESI).

The proportion of subjects in the safety population experiencing an AESI will be compared between the two study treatment arms. Comparisons will be made for at least one AESI of any type, as well as for each of the events that are considered to be of special interest individually. Separate analyses will be performed for AESIs that occur at or before Weeks 12 and 24. AESIs are defined to be any one of herpes zoster, malignancy, serious infection, lymphocytes <500cells mm³, ANC <500cells mm³, AST > 3xULN, ALT > 3xULN, Hy's Law criteria met, Hemoglobin drop > 2mg/dL, increase in HDL/LDL ratio > 50%, or an increase in serum creatinine > 50%.

1.2.4. Secondary Endpoint. Change from Baseline in the Modified Rodnan Skin Score (mRSS).

Change from baseline in the mRSS total score will be compared between the two treatment arms to assess skin thickness relative to the initiation of study treatment at the various time points. The analysis will be performed separately at Weeks 12 and 24 on subjects in the modified intent-to-treat (mITT) population (see section 2.1).

1.2.5. Secondary Endpoint. Provisional American College of Rheumatology Combined Response Index in Systemic Sclerosis CRISS will be compared between the two treatment arms separately at Weeks 12 and 24 on subjects in the modified intent-to-treat (mITT) population (see section 2.1).

1.2.6. Secondary Endpoint. % of Responders as Defined by the mRSS.

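### SAP 1.2.3 and its AESI tables omit gastrointestinal perforation and Hb ≤8 g/dL, and SAP 1.2.3 replaces the LDL-or-HDL criterion with an HDL/LDL ratio

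*SAP*

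**What the plan says.** Protocol 7.5.1 makes AESIs part of the secondary outcome analysis and opens its list with "The adverse events of interest include but are not limited to". The first entry is gastrointestinal perforation: "Patients presenting with new onset abdominal symptoms should be evaluated promptly for early identification of gastrointestinal perforations". Laboratory entries come under a general condition, "Lab value abnormalities compared to screening at any time point and confirmed by repeat testing", and include three on hemoglobin and lipids: "A drop of Hb by >2 gm/dL 6. Hb ≤ 8 gm/dL 7. Increase in LDL or HDL >50" (per cent).

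SAP 1.2.3 instead gives a closed definition: "AESIs are defined to be any one of herpes zoster, malignancy, serious infection", followed by laboratory items that end with "Hemoglobin drop > 2mg/dL, increase in HDL/LDL ratio > 50%, or an increase in serum creatinine > 50" (per cent). It names neither perforation nor an absolute hemoglobin level, and it gives no reference visit or repeat-test condition. The AESI shells (Tables 12 and 29 to 32) also have no row for perforation or for hemoglobin ≤8 g/dL. They print the hemoglobin fall in grams and label the lipid row HDL/LDL, without the word ratio.

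Under SAP 2.3.3, AESI proportions are compared between arms with Fisher's exact test and exact 90% intervals.

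**The concern.** The protocol's open wording allows items to be added, not removed. The SAP removes two and changes the meaning of a third, and gives no reason. Two analysts, one working from each document, could report different counts for the same secondary safety endpoint from the same data.

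The lipid change matters most in substance, because for LDL the new measure points the wrong way: when LDL rises, HDL/LDL falls. Protocol 1.2.5 reports that LDL and HDL both rise on tofacitinib while "Mean LDL/HDL ratios were essentially unchanged in XELJANZ-treated patients". A ratio is therefore a poor detector of the lipid effect that the protocol describes.

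The missing hemoglobin level also matters for dosing. Protocol 7.8 (Laboratory Monitoring) acts on it: "Greater than 2 g/dL decrease or less than 8.0 g/dL: discontinue drug until values have normalized". A subject could have drug held for low hemoglobin and still not appear in the AESI tables.

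**Working it through.** The plan gives no figure to reproduce, so the check is a comparison of texts followed by simple arithmetic.

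**Item by item**

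| Item | Protocol 7.5.1 | SAP 1.2.3 | Tables 12, 29–32 |
|---|---|---|---|
| Gastrointestinal perforation | listed | absent | no row |
| Zoster, malignancy, serious infection | listed | listed | rows present |
| Lymphocytes, ANC, AST/ALT, Hy's law, creatinine | listed | listed | rows present |
| Hb fall | >2 g/dL | >2 mg/dL | >2 g/dL |
| Hb ≤8 g/dL | listed | absent | no row |
| Lipids | LDL or HDL up >50% | HDL/LDL ratio up >50% | HDL/LDL up >50% |
| Reference visit | screening | not stated | not stated |
| Confirmation by repeat test | required | not stated | not stated |

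Counting AST/ALT as one item, the protocol has 12 items and the SAP 10. Eight match, two are altered (Hb fall, lipids) and two are missing.

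**Lipids.** Change in ratio = (1 + HDL change) / (1 + LDL change) − 1.

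- LDL +60%, HDL unchanged: 1/1.60 − 1 = −37.5%. Protocol yes, SAP no.
- LDL +60%, HDL +60%: 1.60/1.60 − 1 = 0%. Protocol yes, SAP no.
- LDL unchanged, HDL +60%: +60%. Both yes.
- LDL −35%, HDL unchanged: 1/0.65 − 1 = +53.8%. Protocol no, SAP yes.
- Mean changes in protocol 1.2.5 (LDL +15%, HDL +10%): 1.10/1.15 − 1 = −4.3%. Neither.

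An LDL fall alone of more than 1 − 1/1.5 = 33.3% would count as an SAP event. With LDL up 50%, HDL would have to rise by more than 1.5 × 1.5 − 1 = 125% before the ratio counted.

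**Hemoglobin.** Take screening as reference, read the fall in g/dL and use a 0.1 g/dL grid. The level criterion is nadir ≤8.0; the fall criterion is screening minus nadir >2.0. Values meeting the first but not the second:

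- Screening 9.0: nadirs 7.0 to 8.0.
- Screening 9.5: nadirs 7.5 to 8.0.
- Screening 9.9: nadirs 7.9 to 8.0.
- Screening 10.0: nadir 8.0 only (fall exactly 2.0).
- Screening 10.1 or more: none (10.1 − 8.0 = 2.1).

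For example, a fall from 9.5 to 7.8 g/dL is 1.7 g/dL. Drug is held because the value is below 8.0. It is a protocol AESI if confirmed, but meets no SAP item.

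Protocol exclusion 28 removes hemoglobin <9 g/dL **or** hematocrit <30%. A subject entering at 9.5 g/dL therefore needs a hemoglobin-to-hematocrit ratio of at most 9.5/30 = 0.317; at 9.0 g/dL, at most 0.300. If the usual ratio is 0.32 to 0.36 (an assumption, not in the documents), hematocrit 30% corresponds to hemoglobin of 0.32 × 30 = 9.6 to 0.36 × 30 = 10.8 g/dL. Most of the 9.0 to 10.0 window is then hard to enter.

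**Reference visit.** With screening 10.4, baseline 9.8 and nadir 7.9 g/dL, the fall is 2.5 from screening but 1.9 from baseline, so the visit is worth naming.

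**Size of one reclassified subject.** In the tofacitinib arm 1/10 is 10 points: the exact 90% interval goes from 0–25.9% (0/10) to 0.5–39.4% (1/10). In the placebo arm 1/5 is 20 points: from 0–45.1% (0/5) to 1.0–65.7% (1/5). Fisher's test rarely changes side: against 0/5, one subject crosses 0.10 only between 5/10 (p = 0.101) and 6/10 (p = 0.044).

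**The case against.** The strongest reply is that most of this is drafting. Much of that stands.

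- **Unit.** A reader might infer that 2 mg/dL (0.002 g/dL) would turn any recorded hemoglobin fall into an AESI. That is not a realistic outcome: all five shells print grams, as does the protocol, so this is a typing slip.
- **Reference and confirmation.** A reader might infer that the SAP abandons both. It is only silent, and protocol 7.5.1 supplies them.
- **Closed list.** An analysis needs one. The fault lies in what this one leaves out.
- **Lipid row.** In the shells AST/ALT stands for AST or ALT, since SAP 1.2.3 lists the two separately. By that convention HDL/LDL could mean HDL or LDL, which is the protocol item. This does not rescue SAP 1.2.3, which says ratio outright. It shows that the SAP is unclear within itself.
- **Visibility.** LDL, HDL and hemoglobin are summarised in Table 33 and plotted in Figures 10, 11 and 1. A perforation that meets SAE criteria would reach the SAE outputs (Table 8, Listing 3) and the independent Medical Safety Monitor (protocol 9.5). It would count in the primary endpoint if Grade 3 or higher by Week 24. Exclusion 24 also makes perforation unlikely. So a reader should not infer that these events would vanish from reporting; they would be missing from the AESI counts.

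**Conclusion.** The point holds as a minor inconsistency with three substantive parts: perforation omitted, hemoglobin ≤8 g/dL omitted, and the lipid criterion replaced in SAP 1.2.3 by a ratio that misses a rise in LDL alone and can count a fall in LDL. Followed as written, the SAP would misclassify some protocol-defined events on a secondary safety endpoint.

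The documents do not support a larger claim. The primary endpoint definition is unaffected. Protocol section 8 treats p-values as hypothesis-generating. The hemoglobin omission matters only for screening values of about 9.0 to 10.0 g/dL with hematocrit of at least 30%, so few subjects are likely to be affected. The documents give no frequency in early dcSSc for any of these cases, so the expected number of reclassified subjects cannot be stated; the effect of one is 10 or 20 points, depending on the arm. The lipid results assume that the word ratio in SAP 1.2.3 is meant, and the hemoglobin results assume screening as reference and a fall measured in g/dL.

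**What to change.** Before unblinding, restate the protocol 7.5.1 list in SAP 1.2.3 and in Tables 12 and 29 to 32:

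- add gastrointestinal perforation;
- add hemoglobin ≤8 g/dL;
- restore the lipid item as a rise of more than 50% in LDL or in HDL, and drop the ratio;
- correct the hemoglobin fall to more than 2 g/dL;
- carry over screening as the reference and confirmation on a repeat test for laboratory items.

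Leave protocol 7.5.1 and 7.8 as they are. The edits restore definitions already in the protocol, so they are not data-driven.

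The cost is one SAP paragraph and two extra rows per shell (with their interval and p-value lines in Tables 29 to 32), plus a relabelled lipid row. No protocol amendment, visit or CRF item is needed, assuming that unscheduled repeat results are in the laboratory data. Separate confirmed and unconfirmed counts are not needed: they would add a count that the protocol does not ask for, and many more lines and tests for 15 subjects.

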2.2 Secondary Outcomes

The **secondary study endpoints** will include:

- Number of Grade 3(severe) or higher adverse events that occur at or before Weeks 12, 36, and 48

- Number of Grade 2 (moderate) or higher adverse events that occur at or before Weeks 12, 24, 36, and 48
- Number of AE's of special interest (AESI) at Weeks 12, 24, 36, and 48
- Change in modified Rodnan Skin Score (mRSS) at Weeks 12, 24, 36, and 48
- Provisional American College of Rheumatology Combined Response Index in Systemic Sclerosis at Weeks 12 , 24, and 48.

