25. Pregnant or breastfeeding female subjects; and female subjects of childbearing potential who are unwilling or unable to use a highly effective method of contraception as outlined in the protocol for the duration of the study and for at least 28 days after discontinuation of study drug.
26. Severe acute or chronic medical or psychiatric condition or laboratory abnormality that may increase risk associated with study participation and in the judgment of the investigator would make the subject inappropriate for entry into this study.
27. History of SSc Renal Crisis within the 6 months prior to baseline.
28. Any of the following lab results at screening:^a
 - Hemoglobin $<9\text{ g/dL}$ or Hematocrit $<30\%$
 - White Blood Cell count $<3.0 \times 10^9/\text{L}$;
 - Absolute Neutrophil count $<1.2 \times 10^9/\text{L}$;
 - White Blood Cell count $<3.0 \times 10^9/\text{L}$;
 - Absolute Neutrophil count $<1.2 \times 10^9/\text{L}$;
 - Platelet count $<100 \times 10^9/\text{L}$;
 - Absolute Lymphocyte count $<0.75 \times 10^9/\text{L}$.
 - ALT or AST $> 1.5 \times$ the upper limit of normal (ULN) of normal at screening or any uncontrolled clinically significant laboratory abnormality that would affect interpretation of study data or the patient's participation in the study
 - Total bilirubin $> \text{ULN}$ at Screening.
 - Estimated glomerular filtration rate [GFR] $<40\text{mL/min}/1.73\text{ m}^2$

29. History of recurrent (more than one episode) herpes zoster or disseminated (at least one episode) herpes zoster, or disseminated (at least one episode) herpes simplex
30. History of any lymphoproliferative disorder, such as Epstein Barr Virus (EBV) related lymphoproliferative disorder, history of lymphoma, leukemia, or signs and symptoms suggestive of current lymphatic disease.
31. History of any malignancy in the last 5 years with the exception of adequately treated or excised basal cell or squamous cell or cervical cancer in situ.
32. History of alcohol or substance abuse, unless in full remission for greater than 6 months prior to first dose of study drug.

^a Please note thresholds for lab parameters indicated throughout this protocol can differ from the published, current package insert due to a new disease and concomitant immunosuppressive therapies.

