# of Safety Patients		
# of AEs		
# of Subjects with AEs		
% of Subjects with AEs		
Severity Grade		
No Adverse Events		
Mild		
Moderate		

[1] Percentages are 100*n/N.

The severity shown is the greatest reported per event for a particular Subject (Mild < Moderate < Severe).

Data cutoff date: DDMMYY

Listing 5: TOFA Listing of Treatment Emergent Adverse Events. Safety Population.

Treatment	Subject ID	New AE Since March 5, 2018	CTCAE Classificaiton	AE Primary Category	AE Start Date	AE End Date	Days from Start of Study Medication	Severity	Relationship to Study Treatment	Outcome	Expected / Unexpected	Study Drug Action Taken	SAE?	Worsening of SSC?

Treatment	Subject ID	New AE Since March 5, 2018	CTCAE Classificaiton	AE Primary Category	AE Start Date	AE End Date	Days from Start of Study Medication	Severity	Relationship to Study Treatment	Outcome	Expected / Unexpected	Study Drug Action Taken	SAE?	Worsening of SSC?

Data cutoff date:DDMMYY

Note: Double-Blind Treatment is expected to last 24 Weeks (168 Days). Those AEs that started >= Day 169 are assumed to have occurred during the Open Label phase.

Table 12: Adverse Events of Special Interest. Safety Population.

Preferred Term Category	Tofacitinib N=10 n (%) [1]	Placebo N=5 n(%) [1]
Total Events		
Total Subjects With At Least One Event		
Herpes Zoster		
Malignancies		
Serious Infections		
Lab Value Abnormalities		
Lymphocytes <500cells mm3		
ANC <500cells mm3		
AST/ALT > 3xULN		
Hy's Law Criteria Met		
Hb drop >2gm/dL		
Increase in HDL/LDL > 50%		
Increase in Serum Creatinine > 50%		

[1] Percentages are 100*n/N. Data cutoff date: DDMMYY

The following set of Figures will be of this format:

[figure not shown]

Figure 1: TOFA Spaghetti Plots of Hemoglobin Over Time by Treatment Figure 2: TOFA Spaghetti Plots of WBC Over Time by Treatment

Figure 3: TOFA Spaghetti Plots of Creatinine Over Time by Treatment

Figure 4: TOFA Spaghetti Plots of Lymphoctyes %Over Time by Treatment

Figure 5: TOFA Spaghetti Plots of Neutrophil % Over Time by Treatment

Figure 6: TOFA Spaghetti Plots of ALT Over Time by Treatment

Figure 7: TOFA Spaghetti Plots of AST Over Time by Treatment

Figure 8: TOFA Spaghetti Plots of Total Cholesterol Over Time by Treatment

Figure 9: TOFA Spaghetti Plots of Triglycerides Over Time by Treatment

Figure 10: TOFA Spaghetti Plots of LDL Over Time by Treatment

Figure 11: TOFA Spaghetti Plots of HDL Over Time by Treatment

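### The SAP's list of adverse events of special interest omits gastrointestinal perforation and Hb ≤8 g/dL and changes the lipid criterion, so it does not match the protocol

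*SAP*

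**What the plan says.** Protocol 2.2 makes the number of events "of special interest (AESI) at Weeks 12, 24, 36, and 48" a secondary endpoint. Protocol 7.5.1 ties its list to that analysis and presents it as a minimum: "The adverse events of interest include but are not limited to". The first item is perforation: "Patients presenting with new onset abdominal symptoms should be evaluated promptly for early identification of gastrointestinal perforations". Herpes zoster, malignancy and serious infections follow. Eight laboratory criteria come last, under the heading "Lab value abnormalities compared to screening at any time point and confirmed by repeat testing". Two of the eight concern hemoglobin and are separate: a drop of more than 2 g/dL, and a value of 8 g/dL or lower. Another is "Increase in LDL or HDL >50"%.

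SAP 1.2.3 says that an AESI is any member of a stated list, and promises a comparison both for at least one AESI and for each type. The list starts with herpes zoster, has no perforation, and closes with "Hemoglobin drop > 2mg/dL, increase in HDL/LDL ratio > 50%, or an increase in serum creatinine > 50"%. The AESI shells (Tables 12 and 29–32) have no row for perforation or for low hemoglobin. Their lipid row reads "Increase in HDL/LDL > 50"%, without the word ratio.

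**The concern.** An SAP has to turn an open-ended list into something programmable, so a fixed list is not a fault in itself. The fault is that this one is shorter than the protocol's minimum and changes one criterion, with no reason given. Because the shells repeat both omissions, this is not a slip in one sentence.

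The lipid wording adds an ambiguity. The SAP text says ratio. The shells use only a slash, and the same shells use a slash for AST/ALT, which SAP 1.2.3 spells out as two separate criteria. Text and shells can therefore be programmed in two ways that give different counts.

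At stake is a secondary safety endpoint in a trial whose primary purpose is safety. Under the SAP text a perforation is not an AESI, and neither is a fall to 8 g/dL or below that is no larger than 2 g/dL. The individual comparisons for these two items disappear whatever the data show.

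**Working it through.** **1. The lists side by side** (protocol 7.5.1; SAP 1.2.3; SAP Tables 12 and 29–32)

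| Item | Protocol | SAP text | SAP shells |
|---|---|---|---|
| Gastrointestinal perforation | yes | no | no |
| Herpes zoster, malignancy, serious infection | yes | yes | yes |
| Lymphocytes <500, ANC <500 | yes | yes | yes |
| AST/ALT >3×ULN, Hy's law | yes | yes | yes |
| Hb drop >2 | g/dL | mg/dL | g/dL |
| Hb ≤8 g/dL | yes | no | no |
| Lipid rise >50% | LDL or HDL | HDL/LDL ratio | HDL/LDL, meaning unclear |
| Creatinine rise >50% | yes | yes | yes |
| Compared with screening, confirmed by repeat | yes | not stated | not stated |

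The mg/dL is a typing error: 2 mg/dL is 0.002 g/dL, and the SAP's own shells use g/dL. The missing repeat-test condition is silence rather than conflict.

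**2. Does the drop rule cover Hb ≤8?** Protocol 4.5, item 28 ("Any of the following lab results at screening"), excludes hemoglobin below 9 g/dL or hematocrit below 30%. For a starting value S and a fall to exactly 8.0, the drop is S − 8.0.

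| S (g/dL) | Drop | Protocol Hb ≤8 | SAP drop >2 |
|---|---|---|---|
| 9.0 | 1.0 | met | not met |
| 9.5 | 1.5 | met | not met |
| 10.0 | 2.0 | met | not met |
| 10.1 | 2.1 | met | met |

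For a fall to exactly 8.0, a start anywhere from 9.0 to 10.0 is missed.

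**3. Is the ratio equivalent to LDL or HDL?** With fractional changes h (HDL) and l (LDL), the ratio changes by (1 + h)/(1 + l) − 1.

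| HDL | LDL | Ratio change | Protocol | SAP ratio |
|---|---|---|---|---|
| 0 | +50% | 1/1.50 − 1 = −33.3% | at threshold | no |
| 0 | +60% | 1/1.60 − 1 = −37.5% | event | no |
| +60% | +60% | 0% | event | no |
| +60% | +15% | 1.60/1.15 − 1 = +39.1% | event | no |
| +20% | −25% | 1.20/0.75 − 1 = +60% | no | event |

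With HDL unchanged, any LDL rise lowers the ratio, so an isolated LDL rise can never be flagged, while an LDL fall of more than one third is flagged. The HDL rise needed to reach the ratio threshold is 1.50(1 + l) − 1. With l = 0.15 this is 1.50 × 1.15 − 1 = 72.5%, against 50% in the protocol. The 15% is the mean LDL rise at 5 mg twice daily in protocol 1.2.5; the other lipid values are illustrative. At the mean changes given there (LDL +15%, HDL +10%) the ratio moves by 1.10/1.15 − 1 = −4.3%.

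**4. Effect of one missed subject with no other AESI.** The 90% Clopper–Pearson interval is the one the SAP specifies.

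| Arm | Protocol definition | SAP definition | Shift |
|---|---|---|---|
| Tofacitinib | 1/10 (0.5–39.4%) | 0/10 (0–25.9%) | 10 points |
| Placebo | 1/5 (1.0–65.7%) | 0/5 (0–45.1%) | 20 points |

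**The case against.** The best opposing case is that little would be lost.

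- **Perforation.** One needing hospitalization fits Grade 3 in protocol 7.4, so with onset by Week 24 it would count in the primary endpoint. Exclusion 24 also removes patients with predisposing lower gastrointestinal conditions. This stands as mitigation, but the AESI analysis would still be wrong.
- **Laboratory values.** Low hemoglobin would show in Table 33 and Figure 1, and lipid values in Table 33 and Figures 10–11. This stands too. It concerns visibility, not classification.
- **Few chances to matter.** Lipids are drawn only at screening and Weeks 6, 30 and 36, so the Week 12 and 24 analyses rest on one scheduled post-screening draw. The hematocrit rule may exclude some patients with hemoglobin between 9 and 10. Both are true, and the documents do not allow the number affected to be estimated.
- **Generic size.** A shift of 10 or 20 points follows from misclassifying any one subject in arms this small. Fisher's test stays above 0.10 in the examples: 1/10 against 0/5 gives p = 1.0, and 0/10 against 1/5 gives p = 5/15 = 0.33. Section 8 of the protocol calls p-values hypothesis-generating. This stands, and it limits the severity.
- **The shells may mean LDL or HDL.** They may. In that case the SAP text is wrong and still needs correcting.

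One argument runs the other way. The protocol endpoint is a number of events, and protocol 8.2.1 plans count comparisons for AESIs. Counts and individual-event rows are affected even in a subject who has another AESI.

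**Conclusion.** The concern holds. The SAP text and the AESI shells omit two events that the protocol names, and the SAP text replaces the lipid criterion with one that is not equivalent and can point the other way. The any-AESI proportion changes only if an affected case occurs in a subject with no other AESI; one such subject is worth 10 points on tofacitinib or 20 on placebo. The separate perforation and low-hemoglobin comparisons are lost in any case. These sizes assume the planned 10 and 5 subjects in the safety population, and the lipid comparison assumes that the word ratio is taken literally. The documents give no basis for a probability that such a case occurs. This should be corrected, but it does not threaten the primary analysis.

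**What to change.** Before unblinding, bring SAP 1.2.3 and Tables 12 and 29–32 into line with protocol 7.5.1:

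- Add gastrointestinal perforation and Hb ≤8 g/dL to the definition and as table rows.
- Replace the ratio with an LDL increase above 50% or an HDL increase above 50%, each against screening. Separate rows make the result readable, and the union is the protocol's single criterion.
- Correct the hemoglobin unit to g/dL.
- Carry over the protocol's comparison with screening and its repeat-test condition. The schedule of events lists no dedicated retest, so also state how an abnormal value without a repeat is handled.
- Leave the cumulative Week 12, 24, 36 and 48 windows as they are. A footnote can give the lipid sampling weeks.

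The cost is SAP wording and shell edits. No new study assessment is needed.
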